12.2.2 Pharmacokinetics (Part A only)

The sample bioanalysis will be performed by Covance. The merging of PK concentration data with actual PK sampling times will be performed by Quintiles Data Management. The PK analysis will be the responsibility of the pharmacokineticist at AstraZeneca. The PK summaries, figures, and data listings, as well as the statistical analysis of the PK variables, will be the responsibility of the Quintiles biostatistician.

All data received will be presented in data listings. Pharmacokinetic summaries will be presented for patients in the PK analysis set, as defined in Section 12.1. Data from patients excluded from the PK analysis set will be included in the data listings, but not in the summaries. Extra measurements (such as unscheduled or repeat assessments) will also not be included in summary tables, but will be included in patient listings.

For qualitative variables, the population size (N for sample size and n for available data) and the percentage (of available data) for each class of the variable will be presented. Quantitative variables will be summarised using descriptive statistics, including n, arithmetic mean, SD, coefficient of variation (%CV), median, minimum, and maximum values. Additionally, geometric means and geometric %CV (%GCV) will be reported for PK variables (concentrations and all PK parameters, except for t_{max}). The geometric mean is calculated as the exponential of the arithmetic mean calculated from data on a log scale. The %GCV is

calculated as $100 \cdot \sqrt{(\exp(s^2) - 1)}$ where s is the SD of the data on a log scale. Mean, SD, CV%, geometric mean, and %GCV will not be calculated for t_{\max} ; t_{\max} will be summarised by median, minimum and maximum values.

For all data, descriptive statistics except for %CV and %GCV will follow the rounding convention of the individual data. Coefficients of variation (%CV and %GCV) will always be reported to 1 decimal place. Ratios and any corresponding confidence intervals (CIs) that are obtained during inferential statistical analysis shall be reported as a percent with 2 decimal places (eg, 99.88).

The PK concentrations will be reported to the same precision as the source data. For descriptive statistics of concentrations, non-quantifiable (NQ) values of plasma concentrations will be handled as follows:

- If, at a given time point, 50% or less of the plasma concentrations are NQ, the mean, SD, geometric mean, %CV, and %GCV will be calculated by substituting the limit of quantification (LOQ) for values which are NQ.
- If more than 50%, but not all, of the concentrations are NQ, the mean, geometric mean, SD, %CV, and %GCV will be reported as not calculable (NC).
- If all the concentrations are NQ, the geometric mean and mean will be reported as NQ and the SD, %CV, and %GCV as NC.

The PK parameters will be rounded for reporting purposes both in the summary tables and by-patient listings. For the calculation of descriptive statistics and the statistical analysis, rounded values as presented in the data listings will be used. Except for raw measurements (such as C_{\max} and t_{\max}), all other derived PK parameters will be reported to 3 significant digits.

The PK data will be presented by hepatic function group (moderate hepatic impairment, mild hepatic impairment or normal hepatic function).

The goal of the statistical analysis in Part A is to estimate the effect of hepatic function on the PK of olaparib. Following log-transformation, C_{\max} and AUC (or AUC_{0-t} , if AUC is not adequately estimable) of olaparib will be separately analysed by analysis of variance (ANOVA), fitting a term for hepatic function group (moderate hepatic impairment, mild hepatic impairment or normal hepatic function).

The analysis will be carried out to compare the ratio of geometric means (gmeans) of the following groups:

1. Child-Pugh A classified patients (mild hepatic impairment) compared to patients with normal hepatic function (controls).
2. Child-Pugh B classified patients (moderate hepatic impairment) compared to patients with normal hepatic function (controls).

The results of these analyses will be presented in terms of geometric means for each hepatic function group. The ratio of geometric means of each hepatically impaired group compared to the normal group (mild/moderate: controls) will be presented with the respective 1-sided 95% upper confidence limit.

The possibility that hepatic impairment has a clinically relevant effect on the exposure of olaparib will be considered if the upper 1-sided 95% confidence limit for the ratio does not lie below the limit of 2, where the limit of 2 implies a doubling in exposure.

Assumptions of normality and constancy of variance will be explored in all analyses and, where necessary, an appropriate transformation (eg. rank) or non-parametric technique (eg. Mann-Whitney test) will be used to validate the results of the main analysis.

An interim analysis will be performed once all patients in the normal hepatic function and mild hepatic impairment groups have completed Part A. The interim PK analysis will be as described above, but limited to a comparison between the normal hepatic function and mild hepatic impairment groups. For details of the interim analysis, see Section [12.2.4](#).

12.2.3 Safety (Part A and Part B)

Safety analyses will be presented using the safety analysis set and will be done by means of descriptive statistics. Safety profiles will be assessed in terms of AEs, vital signs (including BP and pulse rate), ECG, laboratory data (clinical chemistry, haematology, and urinalysis), and physical examination.

Appropriate summaries of AEs, laboratory data, and vital signs will be produced. AEs will be summarised separately for Parts A and B of the study. Laboratory data, vital signs, physical examination, body temperature and ECG will be summarised by hepatic function group (moderate hepatic impairment, mild hepatic impairment or normal hepatic function) and by study day. Summaries will be presented for scheduled visits only. Any unscheduled assessments will be listed. The baseline value is defined as the latest result obtained prior to the start of IP.

The number of patients experiencing AEs following administration of olaparib as well as the number of AEs experienced will be summarised. Adverse events will be classified using the MedDRA system of nomenclature (preferred term and system organ class [SOC]). Adverse events reported before administration of olaparib will be listed only and be referred to as “pre-treatment.” Treatment emergence will be defined for each part of the study (A and B).

For Part A, a treatment emergent AE (TEAE) will be defined as an AE with the start date and time on or after the first dose date and time, and up to (not including) the date and time of the first dose in Part B, or up to (and including) 30 days after dosing in Part A.

For Part B, a TEAE will be defined as an AE with the start date and time on or after the first dose date and time in Part B, and up to (and including) 30 days after the last dose date in the study.

Similarly, the number of patients experiencing SAEs, OAEs, AEs that led to withdrawal, AEs that led to death and treatment-related AEs and the number of such events will be summarised by part, as applicable.

All AE data will be listed for all patients. In addition, SAEs, OAEs, and AEs that led to withdrawal or death, and treatment-related AEs will be listed.

Laboratory data (clinical chemistry, haematology, and urinalysis) will be summarised and listed. Shift tables will be provided for select tests, where shift from baseline to the worst value within each part of the study and overall will be summarised. Laboratory data outside the reference ranges should be indicated in the listings.

Concomitant medications will be summarised by the coded terms. The number of patients receiving a medication will be summarised overall and for each part of the study. A medication taken during the course of the study is considered concomitant. A patient is only counted once if receiving the medication more than once.

The remaining safety variables will be presented using summary statistics for quantitative data and frequency counts for qualitative parameters.

All data will be summarised and listed appropriately.

The impact of any major protocol deviations, missing data, and the use of rescue or concomitant medication on the robustness of study results will be investigated and any methods employed to deal with these will be documented.

Additional tables, figures, or listings may be produced to aid interpretation.

Further details of summaries of the safety data will be given in the SAP.

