6.4.1 Definition of adverse events

An AE is the development of an undesirable medical condition or the deterioration of a pre-existing medical condition following or during exposure to a pharmaceutical product, whether or not considered causally related to the product. An undesirable medical condition can be symptoms (eg, nausea, chest pain), signs (eg, tachycardia, enlarged liver) or the abnormal results of an investigation (eg, laboratory findings, ECG). In clinical studies, an AE can include an undesirable medical condition occurring at any time, including run-in or washout periods, even if no study treatment has been administered.

The term AE is used to include both serious and non-serious AEs.

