Severity of AE

The grading scales found in the revised National Cancer Institute CTCAE (NCI-CTCAE) v4.0 will be utilised for all events with an assigned CTCAE grading ([CTCAE v4.0 2010](#)). For those events without assigned CTCAE grades, the recommendation is the CTCAE criteria that convert mild, moderate, and severe events into CTCAE grades should be used.

A copy of the CTCAE version can be downloaded from the United States Department of Health and Human Services, National Institutes of Health, National Cancer Institute website (http://evs.nci.nih.gov/ftp1/CTCAE/CTCAE_4.03_2010-06-14_QuickReference_5x7.pdf).

For each episode, the highest severity grade attained should be reported.

It is important to distinguish between serious and severe AEs. Severity is a measure of intensity whereas seriousness is defined by the criteria in Section [6.4.2](#). An AE of severe intensity need not necessarily be considered serious. For example, nausea that persists for several hours may be considered severe nausea, but not a SAE. On the other hand, a stroke that results in only a limited degree of disability may be considered a mild stroke but would be a SAE.

Causality collection

The Investigator will assess causal relationship between IP and each AE, and answer ‘yes’ or ‘no’ to the question ‘Do you consider that there is a reasonable possibility that the event may have been caused by the investigational product?’

Causal relationship will also be assessed for other medication and study procedures. Note that for AEs that could be associated with any study procedure the causal relationship is implied as ‘yes’.

For a guide to the interpretation of the causality question, see [Appendix B](#) to the Clinical Study Protocol.

Adverse Events based on signs and symptoms

All AEs spontaneously reported by the patient or reported in response to the open question from the study personnel, “Have you had any health problems since the previous visit?” or revealed by observation will be collected and recorded in the CRF. When collecting AEs, the recording of diagnoses is preferred (when possible) to recording a list of signs and symptoms. However, if a diagnosis is known and there are other signs or symptoms that are not generally part of the diagnosis, the diagnosis and each sign or symptom will be recorded separately.

Adverse Events based on examinations and tests

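### Treatment emergence rests on AE start date alone, so an AE ongoing across a part's first dose that then worsens is not counted in the part where it worsened

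*Protocol*

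**What the plan says.** The protocol fixes the rule in section 12.2.3 and leaves only further summary detail to the SAP. For the single-dose part, with the Part A dose as the reference point: "For Part A, a treatment emergent AE (TEAE) will be defined as an AE with the start date and time on or after". One end of its window reads "and up to (not including) the date and time of the first dose in Part B"; the alternative end reads "or up to (and including) 30 days after dosing in Part A". For the continuous part: "For Part B, a TEAE will be defined as an AE with the start date and time on or after the first dose date" in that part, and to 30 days after the last dose in the study. Events before any drug are set aside: "Adverse events reported before administration of olaparib will be listed only". Neither definition mentions an increase in grade.

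Section 6.4.3 starts AE collection at consent. For each AE it collects one start, one stop and the maximum CTCAE grade reached. Under severity it adds: "For each episode, the highest severity grade attained should be reported". The listed variables include the date on which an event became serious, but no date for a change of grade.

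Section 6.4.1 counts as an AE "the deterioration of a pre-existing medical condition following or during exposure to a pharmaceutical product". Section 6.4.3 also makes a new or aggravated physical finding, compared with baseline, an AE.

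**The concern.** The secondary objective (section 2.2) is the safety of single and of multiple doses by hepatic function, with AEs graded by CTCAE. Section 12.2.3 serves it by summarising AEs separately for Parts A and B. That split is informative only if an event is counted in the period in which it became a problem.

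With an onset-only rule and one record per episode, a mild event that straddles a first dose keeps its early start date whatever happens later. Worsening on twice-daily olaparib can then be missing from the Part B summary, and an event that peaked on continuous dosing can be counted under one dose. Such straddling events are to be expected. Screening runs from up to 28 days before dosing (Table 4), with AEs collected from consent, and Part B begins only 5 to 14 days after the Part A dose (section 3.1).

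**Working it through.** The protocol gives no figure to reproduce. The check is to apply the rule in 12.2.3 to each kind of worsening, using only what 6.4.1 and 6.4.3 say is recorded.

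1. **AE starts between consent and the Part A dose, then worsens on drug; kept as one record.** The start precedes the first dose of both parts, so it is a TEAE in neither. It is listed only.

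2. **AE starts between the Part A dose and the first Part B dose, then worsens on continuous dosing; kept as one record.** The start falls in the Part A window, so it is a Part A TEAE. The start precedes the first Part B dose, so it is not a Part B TEAE. Its one stored grade is the maximum, and any tabulation by grade puts that maximum under the single dose. Sections 9.5 and 12.2.1 add a dependence on timing. Part A is locked and reported on its own, with Part B in an addendum. If the worsening comes after the Part A lock, the Part A report holds the lower grade and Part B still leaves the event out.

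3. **The same event starts just after the first Part B dose.** It is a Part B TEAE. Cases 2 and 3 can differ by a day in onset and be identical in what happened on continuous dosing.

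4. **A baseline condition from the medical history worsens after dosing.** Under 6.4.1 the deterioration is itself an AE. It can be entered with a post-dose start and is then counted.

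5. **A laboratory value worsens.** Section 12.2.3 provides shift tables for selected tests, from baseline to worst value, by part and overall.

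The rule therefore fails in cases 1 and 2, and only if the worsening stays in the existing record. The protocol does not define an episode or say whether a rise in grade opens a new record. Section 6.4.1 leans towards a new record and the one-grade-per-episode rule in 6.4.3 towards keeping the old one.

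**Size of one misplaced patient.** AE summaries use the safety set, which is everyone dosed with any post-dose data (section 12.1). About 30 patients are to be enrolled in 3 groups (section 12.3).
- Assuming all are dosed and evenly spread: 30/3 = 10 per group, and 1/10 = 10 percentage points.
- At the PK-evaluable minimum of 8 per group: 1/8 = 12.5 percentage points.

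**Part A window.** The text joins its two end points with 'or' and does not say which applies to whom. If the 30-day limit were applied to patients who continue, the Part A and Part B windows would overlap by 30 − 14 = 16 to 30 − 5 = 25 days. Footnote a of Table 4 ties the Part A follow-up visit to patients who withdraw early or do not enter Part B. The intended reading is thus fairly clear, but 12.2.3 does not state it.

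**The case against.** The best defence is that the protocol already captures most worsening. Low-grade fatigue, ascites or nausea present at entry is a baseline condition, and sections 6.4.1 and 6.4.3 allow its deterioration to enter as a new AE. All AEs are listed for every patient. SAEs, events leading to withdrawal or death, and treatment-related events are also listed separately. The CRF dates the onset of seriousness, and section 5.10 has every dose reduction and interruption recorded with its reason. With about 30 patients, listings can be read one by one. Nothing forbids a new record when an event worsens.

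Most of this stands, and it limits the point. A reader might infer that on-drug worsening is generally dropped from reporting. The documents do not support that: the gap is in TEAE counts, for AEs already on record at a first dose. The defence does not close that gap. Listings do not restore an event to a count by part, the shift tables cover selected laboratory tests and not symptoms, and sites may differ on whether worsening opens a new record.

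A reader might also infer that the unequal Part A windows bias the comparison between hepatic groups. Calendar time at risk does differ, by 30/14 = 2.1 to 30/5 = 6 times between patients who stop and those who continue. But bias between groups needs a difference in Part B uptake, which is unknown, and the safety analysis is descriptive. The tablet half-life quoted in section 1.1.3.2 is 5 to 9 hours, so the calendar ratio overstates any difference in drug exposure. Ending the Part A window once continuous dosing starts is also reasonable in itself.

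**Conclusion.** The point holds in a limited form. Section 12.2.3 states an onset-only rule, and the data described in 6.4.3 carry no date for a change of grade. An AE ongoing at the first dose of a part that worsens afterwards, if kept as one record, is left out of that part's TEAE summary. If it began after the Part A dose, it is counted under the single dose instead, even if its maximum grade was reached on continuous dosing. This works against the comparison of single- and multiple-dose safety in the secondary objective.

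The conclusion assumes that worsening stays in the existing record, which the protocol neither requires nor excludes. The share of such events is not given, so the total effect cannot be sized. One patient moves a group's incidence by about 10 percentage points if 30 dosed patients are evenly spread. The 12.5-point figure applies only at 8 per group, the PK-evaluable minimum and not the safety set. Part B denominators are unknown because entry is optional.

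**What to change.** - **Section 12.2.3:** for each part, define a TEAE as an AE that starts, or worsens in CTCAE grade, on or after the first dose of that part. State that the 30-day Part A limit applies only to patients who do not enter Part B.
- **Section 6.4.3:** require that a grade increase in an AE ongoing at the first dose of either part be recorded with its own date and grade. Restricting this to AEs ongoing at a first dose avoids a new entry for every fluctuation.
- **Optional:** a Part A summary limited to the time from dose to the earliest permitted Part B start, which is common to all patients who complete Part A.

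The cost is a change of wording and a CRF completion instruction, with slightly more AE records and somewhat higher Part B counts. No dose or clinical rule changes.

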12.2.4 Interim analysis

An interim analysis will be performed to compare the PK, safety and tolerability of olaparib in subjects with mild hepatic impairment to those with normal hepatic function. Any patients enrolled into the moderate hepatic impairment group at the time of data-cut off for this interim analysis will be listed but not summarised.

The data will be displayed, in both the tables and listings, by hepatic group and will include a total column for an overall summary. Summary tables will display mild hepatic impairment and normal hepatic function while listings will also display the moderate hepatic impairment group.

The PK analyses performed during the interim analysis will compare the normal hepatic function and mild hepatic impairment groups only, but will otherwise be the same as those described for the final analysis of Part A data in Section [12.2.2](#).

12.3 Determination of sample size

The study has been sized to provide adequate PK information to assess the effects of hepatic impairment on the PK of olaparib, whilst exposing as few patients as possible to the IP and procedures. Based on the estimate of between-patient standard deviation (SD) for log AUC from Study D0810C00024 of 0.531, including 8 patients per arm provides approximately 80% chance that a 1-sided 95% confidence interval would exclude the possibility of a doubling in AUC.

Approximately 30 patients with advanced solid tumours will be entered to ensure that at least 24 evaluable patients complete the study (8 patients with normal hepatic function, 8 with mild hepatic impairment [Child-Pugh A] and 8 with moderate hepatic impairment [Child-Pugh B]). An evaluable patient is defined as a patient having full PK sampling to 96 hours post dose of olaparib.

12.4 Data monitoring committee (Not applicable)

13. IMPORTANT MEDICAL PROCEDURES TO BE FOLLOWED BY THE INVESTIGATOR

13.1 Medical emergencies and AstraZeneca contacts

The PI is responsible for ensuring that procedures and expertise are available to handle medical emergencies during the study. **A medical emergency usually constitutes an SAE and is to be reported as such, see Section 6.4.4.**

In the end of a medical emergency the Investigator may contact the 24-hour Quintiles Medical Emergency Contact Centre [REDACTED]

13.2 Overdose

There is currently no specific treatment in the event of overdose of olaparib and possible symptoms of overdose are not established.

Adverse reactions associated with overdose should be treated symptomatically and should be managed appropriately.

- An overdose with associated AEs is recorded as the AE diagnosis/symptoms on the relevant AE modules in the CRF and on the Overdose CRF module.
- An overdose without associated symptoms is only reported on the Overdose CRF module.

If an overdose on an AstraZeneca IP occurs in the course of the study, then investigators or other study site personnel should inform appropriate AstraZeneca representatives immediately, or **no later than 24 hours** of when he or she becomes aware of it.

The designated AstraZeneca representative works with the investigator to ensure that all relevant information is provided to the AstraZeneca Patient Safety data entry site.

For overdoses associated with SAE, standard reporting timelines apply, see Section 6.4.4. For other overdoses, reporting should be done within 30 days.

13.3 Pregnancy

All outcomes of pregnancy should be reported to AstraZeneca or its representative.

13.3.1 Maternal exposure

If a patient becomes pregnant during the course of the study, olaparib should be discontinued immediately.

Pregnancy itself is not regarded as an AE unless there is a suspicion that the IP under study may have interfered with the effectiveness of a contraceptive medication. Congenital abnormalities/birth defects and spontaneous miscarriages should be reported and handled as SAEs. Elective abortions without complications should not be handled as AEs. The outcome of all pregnancies (spontaneous miscarriage, elective termination, ectopic pregnancy, normal birth or congenital abnormality) should be followed up and documented even if the patient was discontinued from the study.

If any pregnancy occurs in the course of the study, then investigators or other site personnel inform appropriate AstraZeneca representatives immediately, or **no later than 24 hours** of when he or she becomes aware of it.

The designated AstraZeneca representative works with the investigator to ensure that all relevant information is provided to the AstraZeneca Patient Safety data entry site within 1 or 5 days for SAEs, see Section 6.4.4, and within 30 days for all other pregnancies.

The same timelines apply when outcome information is available.

